9.5.2. Efficacy Analyses

The primary endpoint for efficacy analyses is the ORR, by central review. For Group 1 and Group 3 patients in which all response assessments are done by RECIST 1.1 (Eisenhauer 2009) analysis of radiologic scans, the independent radiology review is the central review. For Group 2 patients (and some Group 1 and Group 3 patients), response assessments include photos and radiologic scans, and the independent composite review committee will serve as the central review.

The primary analyses of efficacy are based on the binomial exact confidence interval approach, ie, whether the lower limit of 95% confidence interval will exclude a historical control ORR that is not deemed clinically meaningful. The 95% binomial exact confidence intervals using Clopper-Pearson method (Clopper 1934) for observed ORRs are listed for Groups 1 and 3 (Table 10), Group 2 (Table 11), Group 4 (Table 12), and Group 6 (Table 13).

The investigator-assessed ORR will be considered as a secondary analysis. Patients who are deemed as not evaluable according to RECIST 1.1 or inevaluable by the composite efficacy criteria will be considered as not reaching PR/CR for ORR (see Section 6.3.2).

The secondary efficacy endpoints as measured by DOR, PFS, and OS will be summarized by median and its 95% confidence interval by the Kaplan-Meier method.

The CR rate will be summarized descriptively with 95% confidence interval. Absence of residual CSCC in patients with locally advanced CSCC achieving a clinical response to cemiplimab, as measured by central review, will be summarized descriptively.

On an exploratory basis, efficacy data between different groups may be described. Such analyses should be performed so that each group has a similar amount of follow up (for example, at time of primary analysis, which is pre-specified as last patient first dose (LPFD) plus approximately 6 months for each group.)

Amendment 9: For Group 6 patients who opt to switch to SC cemiplimab, efficacy data per central review will be censored at the first SC dose. Because Group 6 patients are only allowed to switch to SC cemiplimab after completing at least 27 weeks on study (3 tumor assessments after baseline), which is the pre-specified timepoint for primary efficacy analyses in Group 6, switching to SC dosing will have no impact on the primary efficacy analysis for Group 6.

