APPENDIX 10. STATISTICAL ANALYSES

ESTIMANDS

For Group 6 primary analysis, the statistical methods for the primary and secondary endpoints will be consistent with that which was done for Groups 1 to 3. This will facilitate a meaningful comparison of Group 6 with the previous groups. Additional statistical analyses will also be performed, including sensitivity analyses for DOR and PFS assuming informative censoring for intercurrent event.

Attributes for ORR per Central Review and Investigator Assessment

1. The study population is defined as CSCC patients who are enrolled on the protocol.
2. The endpoint is ORR, defined as the proportion of patients with BOR of CR or PR. ORR per central review is the primary endpoint, and ORR per investigator assessment is a secondary endpoint.
3. Intercurrent events and how to account for these events are described in [Table 16](#).
4. Estimated ORR will be provided, along with the 2-sided 95% exact binomial confidence interval using the Clopper-Pearson method.

Table 16: Intercurrent Events for Analysis of ORR per Central Review and Investigator Assessment

Intercurrent events	Rules of imputing data in primary analysis
Initiation of palliative radiation therapy	Patient will be considered to have PD at time of initiation of radiation (Section 5.7.4 of protocol).
Surgical removal of target lesion	BOR will be considered as PR if no prior PD is observed (Section 5.7.3 of protocol).
Unconventional responses (eg, a patient first experience PD and then CR or PR)	BOR will be considered as PD.
No evaluable postbaseline tumor assessment	BOR will be deemed NE. Patient with BOR of NE will be included in the ORR analysis as a non-responder.

A sensitivity analysis will be performed for ORR where the intercurrent events of “initiation of palliative radiation therapy” and “surgical removal of target lesion” will be ignored. Patients with unconventional responses will be considered as responders. Patients with BOR of NE will be excluded from this analysis.

Attributes for DOR per Central Review and Investigator Assessment

1. The study population is defined as CSCC patients who are enrolled on the protocol and had a CR/PR response.
2. The endpoint is DOR, measured from the time measurement criteria are first met for CR/PR (whichever is first recorded) until the first date of recurrent or progressive disease or death due to any cause in patients with BOR of CR or PR.

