Group 6 patients will receive up to twelve 63-day (9-week) treatment cycles for up to 108 weeks of treatment. Each patient will receive 350 mg cemiplimab intravenously on days 1, 22±3, and 43 ±3 during each treatment cycle. Tumor assessments will be made at the end of each treatment cycle. Extensive safety evaluations will occur on day 1 of each cycle, with routine safety evaluations to be conducted at each cemiplimab dosing visit. After implementation of PA9, patients will be given the option to receive subsequent doses of cemiplimab SC. The first 12 patients who opt to switch to SC will receive cemiplimab [REDACTED]. The next ≥6 patients who opt to switch to SC will receive cemiplimab [REDACTED]. Group 6 patients will have the option to switch to SC dosing or to remain on 350 mg Q3W IV dosing.

A patient will receive treatment until the treatment period (96 weeks in Group 1 and Group 2; 54 weeks in Group 3; 48 weeks in Group 4; 54 weeks in Group 5; 108 weeks in Group 6) is complete, or until disease progression, unacceptable toxicity, withdrawal of consent, or confirmed complete response (CR). Group 1 and Group 2 patients with confirmed CR after a minimum of 48 weeks of treatment and Group 6 patients with confirmed CR after a minimum 54 weeks of treatment may elect to discontinue treatment and continue with all relevant study assessments (eg, efficacy assessments).

Groups 1 through 5: Patients in all groups who do not experience progressive disease (PD) will be followed for an additional nontreatment period of up to approximately 6 months with scans performed every 8-12 weeks. After completion of this follow-up period, patients will then enter an extended follow-up period for approximately 1 additional year with assessments every 4 months. Patients in Groups 1 to 5 who complete treatment without disease progression and subsequently experience disease progression during the follow-up period without any intervening systemic anticancer therapy, are eligible for up to 2 years of retreatment with cemiplimab 350 mg IV Q3W.

Group 6: Patients who do not experience PD at the completion of the planned treatment period will enter follow-up for approximately 6 months. There is no extended follow-up for Group 6. Patients enrolled in Group 6 are not eligible for retreatment.

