5.9. Analysis of Safety Data

The analysis of safety and tolerance will be performed on the SAF, as defined in Section 3.2.

The safety analysis will be based on the reported AEs and other safety information (clinical laboratory evaluations, vital signs and 12-lead ECG). The analysis will comprise the basis upon which conclusions will be drawn regarding the cemiplimab. The AE of special interest will be determined by the list provided by medical monitors.

Period of observation: The observation period will be divided into three segments: pre-treatment, on-treatment and post-treatment.

- The pretreatment period is defined as the time from signing the ICF to before the first dose of study drug.
- The on-treatment period is defined as the day from the first dose of study drug to 105 days after the last dose of study drug or to follow-up visit, whichever is longer. For patients who started cemiplimab as re-treatment more than 30 days after their last regular cemiplimab treatment, the on-treatment period ends at the earlier day of 105 days after the last regular cemiplimab dose or 1 day before their first dose of cemiplimab re-treatment.
- The post-treatment period is defined as the time starting 1 day after the on-treatment period.

Day 1 is the first day of patient receiving cemiplimab treatment, Day –1 is the day before, and there is no Day 0.

The safety analysis will be concentrated on events that occur during on-treatment period. Events that occur during post-treatment period, or during cemiplimab re-treatment will be listed and summarized if necessary.

The summary of safety results will be presented by group and combined.

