5.9.1. Adverse Events

The verbatim text, the primary system organ class (SOC), and the preferred term (PT) will be displayed in subject listings. Summaries that include frequencies and proportions of patients reporting AEs will include the SOCs and the PTs.

Definitions:

- Pre-treatment AEs are defined as AEs that developed during the pre-treatment period.
- Treatment-emergent AEs (TEAEs) are defined as AEs that developed or worsened during the on-treatment period and any immune-related AEs that occurs any time after the first dose of cemiplimab.
- Post-treatment AEs are defined as AEs that developed or worsened during the post treatment period and are not considered drug related by the investigator.

The focus of adverse event reporting in the CSR will be on TEAEs. For details on handling missing data and partial dates, see Section 6.

Summaries of AEs will include: TEAEs, Treatment related TEAEs, Serious TEAEs, Treatment-related Serious TEAEs, AESI, immune-related AEs, and infusion related AEs. For TEAEs, the following will be summarized:

- The number and proportions of patients reporting at least 1 TEAE, presented by SOC and PT
- TEAEs by severity (CTCAE, version 4.03 grade), presented by SOC and PT
- TEAEs related to treatment, presented by SOC and PT
- TEAEs occurring in $\geq 5\%$ patients, presented by PT
- TEAEs leading to permanent treatment discontinuation, presented by SOC and PT
- TEAEs leading to death, presented by SOC and PT

For each TEAE summary presented by SOC and PT, the summary table will be sorted by decreasing frequency of SOC and PT. For TEAE summary presented by PT, the summary table will be sorted by decreasing frequency of PT.

The irAEs reported by investigator will be summarized. Additionally, irAEs identified by the sponsor will be summarized. All irAEs occurred during the on-treatment and post-treatment period will be included.

For AE listings, the following variables will be displayed:

- Age/Gender
- Verbatim Term, SOC, PT
- AE start date and end date/ongoing (and corresponding study day)
- AE duration
- Relationship to study drug: unrelated or related
- Seriousness (Serious AE or not)
- National Cancer Institute-Common Terminology Criteria for Adverse Events (NCI CTCAE) grade
- Action taken
- Treatment for AE
- Outcome

Counts will be provided for each patient within each SOC and PT. Percentages will be calculated using the number of patients from the SAF in each group.

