5.9.2. Clinical Laboratory Measurements

Listings of laboratory measurement will include laboratory values, normal ranges, grade (if applicable), collection date, and visit/cycle. The numeric lab variables and change from

baseline to each visit/cycle will be summarized. Listings of abnormal lab values and clinically significant (Yes/No) by patient and visit/cycle will also be constructed.

Summary tables for worst laboratory values with NCI CTCAE v4.03 all grade and grade ≥ 3 observed during on-treatment period will be generated. Summary of Shift tables from baseline to worst NCI CTCAE v4.03 grade observed during on-treatment period will be generated.

The shift tables include:

- Overall and individual Hematologic Test (Hemoglobin, Platelets, WBC)
- Overall and individual Liver Function Test: (AST, ALT, ALP, Total Bilirubin and Albumin)
- Overall and individual Electrolytes (Sodium, Potassium, Magnesium, Calcium, Chloride, Bicarbonate, Phosphorus)

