11. APPENDIX

11.1. Summary of Statistical Analyses

Efficacy Analysis:

Endpoint	Analysis Populations	Primary Analysis	Statistical Method	Supportive Analysis	Subgroup Analysis	Other Analyses
Primary Endpoint						
ORR	FAS	Proportion of patients with best overall response of CR or PR (central review)	95% exact binomial confidence interval using Clopper-Pearson method	Exact binomial test p-value	Yes	Yes
Secondary Endpoints						
ORR	FAS	Proportion of patients with best overall response of CR or PR (investigator review)	95% exact binomial confidence interval using Clopper-Pearson method	Exact binomial test p-value	No	No
Duration of response	Patients with best overall response of CR/PR in FAS	From the time measurement criteria are first met for CR/PR (whichever is first recorded) until the first date of recurrent or progressive disease (radiographic), or death due to any cause.	Kaplan-Meier method and descriptive statistics	No	Yes	No
Progression-free survival	FAS	From the start of treatment until the first date of recurrent or progressive disease (radiographic), or death due to any cause.	Kaplan-Meier method	No	No	No
Overall survival	FAS	From the start of treatment until death due to any cause.	Kaplan-Meier method	No	No	No
Quality of life	FAS	Changes scores from day 1 of EORTC-QLQ-C30	Descriptive statistics and longitudinal plots	No	No	No

Safety Analyses:

Endpoint	Analysis Populations	Primary Analysis	Statistical Method	Supportive Analysis	Subgroup Analysis	Other Analyses
Adverse Events	SAF	Percent of patients by system organ class and PT	Descriptive Statistics	No	No	No

Signature Page for VV-RIM-00330503 v1.0

Approval/eSignature	 12-Dec-2023 22:56:28 GMT+0000
---------------------	---

Approval/eSignature	 13-Dec-2023 02:12:18 GMT+0000
---------------------	---

Approval/eSignature	 13-Dec-2023 03:02:56 GMT+0000
---------------------	---

Signature Page for VV-RIM-00330503 v1.0 Approved

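### Adverse events and graded laboratory toxicity are planned only as crude on-treatment percentages and worst grades, by group and combined, although planned treatment runs from 48 to 108 weeks; later safety tables will tend to mix event rate with planned duration.

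*SAP*

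**What the plan says.** SAP 5.9.1 opens its list of treatment-emergent adverse event (TEAE) tables with "The number and proportions of patients reporting at least 1 TEAE, presented by SOC and PT" and fixes the denominator: "Percentages will be calculated using the number of patients from the SAF in each group". The safety row of SAP 11.1 names one measure, "Percent of patients by system organ class and PT", with descriptive statistics and no supportive or other analysis. SAP 5.9 adds: "The summary of safety results will be presented by group and combined".

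For laboratory data, SAP 5.9.2 plans "Summary tables for worst laboratory values with NCI CTCAE v4.03 all grade and grade" 3 or higher during the on-treatment period, as well as summaries by visit or cycle.

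SAP 2.3 gives planned treatment as 96 weeks in Groups 1 and 2, then "54 weeks in Group 3; 48 weeks in Group 4; 54 weeks in Group 5; 108 weeks in Group 6". Under SAP 5.9 the on-treatment period runs from first dose to 105 days after the last dose, or to the follow-up visit if that is later. Immune-related events (irAEs) are the exception: SAP 5.9.1 counts them at any time after first dose.

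SAP 5.7 summarizes exposure duration by group but does not link it to the adverse event percentages. Neither document plans an exposure-adjusted rate, a time-to-first-event analysis, or an adverse event table over a common period. For exploratory descriptions of efficacy across groups, Protocol 9.5.2 does set a condition: "Such analyses should be performed so that each group has a similar amount of follow up". Safety has no counterpart.

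**The concern.** The percentage of patients with at least one event rises with the time over which events are counted. A worst grade rises with both time and the number of samples. Here the counting period is tied to treatment length, and treatment length is set by group. When groups stand side by side, a lower percentage in Group 3 or 4 could reflect a lower event rate or only a shorter course, and the planned tables cannot separate the two. Groups 3 and 6 show this most plainly: both are assigned 350 mg IV every 3 weeks, with planned courses of 54 and 108 weeks. The combined column has no single observation period to which its percentage refers.

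Safety is part of Group 6's primary objective, and the SAP states that collection of safety data continues after the primary efficacy analysis. The tables most exposed to the problem are therefore ones that will be produced.

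**Working it through.** **Planned weeks (cycles × cycle length, SAP 2.3).** Groups 1 and 2: 12 × 8 = 96. Groups 3 and 5: 6 × 9 = 54. Group 4: 6 × 8 = 48. Group 6: 12 × 9 = 108. These match the SAP.

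**Window for a patient who takes exactly the planned course.** Week of last dose = (number of doses − 1) × dosing interval. Add 105 days = 15 weeks.

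| Group | Doses | Last dose, week | Window, weeks |
|---|---|---|---|
| 1, 2 | 48 | 47 × 2 = 94 | 109 |
| 3, 5 | 18 | 17 × 3 = 51 | 66 |
| 4 | 12 | 11 × 4 = 44 | 59 |
| 6 | 36 | 35 × 3 = 105 | 120 |

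Hematology and chemistry are drawn at each dosing visit, so the dose counts are also the planned numbers of draws from which a worst grade is taken.

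**Expected crude percentage at one common rate.** The documents give no event rate or stopping rate, so both are assumed and equal in all groups. Let λ be the weekly event rate, d the weekly stopping rate, and T the week of the last planned dose. Time on drug is the smaller of an exponential time and T, and the window adds 15 weeks:

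P = 1 − exp(−15λ) × [d + λ·exp(−(d+λ)T)] / (d+λ)

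With 10% one-year risk, λ = −ln(0.9)/52 = 0.002026. With a median of 52 weeks on drug, d = ln 2/52 = 0.01333. For Group 6, exp(−15λ) = 0.9701 and exp(−0.015356 × 105) = 0.1994, so P = 1 − 0.9701 × (0.01333 + 0.002026 × 0.1994)/0.015356 = 13.2%. The other groups, and other stopping rates:

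| Median on drug | Groups 1, 2 | Groups 3, 5 | Group 4 | Group 6 |
|---|---|---|---|---|
| 26 weeks | 9.4% | 8.3% | 7.9% | 9.5% |
| 52 weeks | 12.8% | 9.9% | 9.3% | 13.2% |
| 104 weeks | 15.6% | 11.1% | 10.2% | 16.5% |

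At 52 weeks the combined figure, weighted by the patient numbers in Protocol 4.1 (59 + 78, 56 + 9, 63 and a planned 167; total 432), is (137 × 12.8 + 65 × 9.9 + 63 × 9.3 + 167 × 13.2)/432 = 12.0%. It describes no group's observation period.

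**A fixed threshold.** SAP 5.9.1 lists TEAEs seen in at least 5% of patients. With 4% one-year risk and the same stopping rate, the formula gives 5.4% in Group 6 and 3.7% in Group 4. If the threshold is applied within group, the event is listed in one and not in the other.

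**Where the gap closes.**
- *Early data cut.* Take a cut 26 weeks after the last patient's first dose, uniform accrual, no stopping and 0.2 events per patient-year. Group 4 against Group 6 is 13.9% against 13.9% with 26 weeks of accrual, 16.9% against 18.0% with 52 weeks, and 18.1% against 21.8% with 78 weeks.
- *Early-clustered events.* If all risk ends at week 24 and nobody stops before then, every group shows 1 − exp(−0.2 × 24/52) = 8.8%.

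**The measure proposed below.** Counting onset only to week 48 caps T at 48 − 15 = 33 in the formula for every group. In the 52-week example all groups then give 8.1%, as they should at a common rate.

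**The case against.** The strongest case is that this is a matter of presentation. The groups are not randomized, SAP 2.1 has them analyzed independently, and no formal between-group safety comparison is planned. Exposure is tabulated by group, listings carry study day, and numeric laboratory values are summarized by visit. In the central example the gap between Groups 6 and 3 is about 3 points, while sampling error on that difference with 167 and 56 patients is about ±9 points. All of this is correct, and it limits the weight of the point. It does not remove it: the exposure table shows the imbalance without correcting it, and the distortion pushes event types with a continuing hazard the same way.

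Four stronger readings are tempting, and the documents do not support them.
- *Week 66 as the end of observation in Group 3, or a two-fold gap in maximum window.* Protocol 6.3.6 lets patients in Groups 3 to 5 without progression, if unwilling to stop, continue through cycles 7 to 12. A Group 3 patient who does so has the same last-dose week as Group 6. The windows above describe the planned course, not a limit.
- *Appendix 10 as a planned safety comparison.* Its sentence "This will facilitate a meaningful comparison of Group 6 with the previous groups" stands under estimands, and the appendix defines only response rate, duration of response, progression-free survival and overall survival.
- *irAEs as equally affected.* They count at any time after first dose. Visit follow-up without progression is about 54 + 26 + 52 = 132 weeks in Group 3 and 108 + 26 = 134 in Group 6. However, Protocol 7.2.1 limits reporting after 105 days to serious events or events of concern thought to be related, so later capture is thinner.
- *The gap as present in every table.* At the primary cut it is small or nil.

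**Conclusion.** The concern holds in a limited form. The only planned adverse event measure is a crude percentage, and graded laboratory toxicity is a worst on-treatment grade, over windows that depend on planned treatment length. In safety tables made after the primary data cut, Groups 3, 4 and 5 will tend to show lower percentages than Groups 1, 2 and 6 at the same event rate, and the combined column will average unequal windows.

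The size rests on assumptions. With a constant rate, 10% one-year risk and a median of 52 weeks on drug, it is about 13% in Group 6 against 9% to 10% in Groups 3 and 4. At a median of 26 weeks the gap between Groups 6 and 4 falls to 1.6 points (9.5% against 7.9%). Early-clustered events and continuation past the planned period reduce it further, the latter by an unknown amount. This is a weakness in how later safety tables can be read. It is not an error in a test, an endpoint or a decision rule.

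**What to change.** In SAP 5.9.1, keep the crude tables. For TEAEs, TEAEs of grade 3 or higher, serious TEAEs and TEAEs leading to treatment discontinuation, add by group and combined:

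1. patients with a first event per 100 patient-years at risk in the on-treatment window;
2. the percentage with onset by a common time, for example week 48, which is the shortest planned treatment and lies inside every planned-course window. State how patients with less than 48 weeks of potential follow-up at the data cut are handled.

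For irAEs, keep the SAP's definition, compute person-time over that same period (any time after first dose), and also give the percentage by the common time.

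In SAP 5.9.2, add worst-grade laboratory tables over the same common period. State that any between-group safety remark will rest on these measures and not on the crude percentages.

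The cost is SAP wording and a few extra tables from dates already collected, with no change to study conduct. The rate in (1) assumes a roughly constant hazard, which is why (2) accompanies it. The common-period percentage leaves out later events, which the retained crude tables still show.

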5.9.2. Clinical Laboratory Measurements

Listings of laboratory measurement will include laboratory values, normal ranges, grade (if applicable), collection date, and visit/cycle. The numeric lab variables and change from

baseline to each visit/cycle will be summarized. Listings of abnormal lab values and clinically significant (Yes/No) by patient and visit/cycle will also be constructed.

Summary tables for worst laboratory values with NCI CTCAE v4.03 all grade and grade ≥ 3 observed during on-treatment period will be generated. Summary of Shift tables from baseline to worst NCI CTCAE v4.03 grade observed during on-treatment period will be generated.

The shift tables include:

- Overall and individual Hematologic Test (Hemoglobin, Platelets, WBC)
- Overall and individual Liver Function Test: (AST, ALT, ALP, Total Bilirubin and Albumin)
- Overall and individual Electrolytes (Sodium, Potassium, Magnesium, Calcium, Chloride, Bicarbonate, Phosphorus)

